The Effect of Gastric Acid Suppression on Probiotic Colonization

Study Protocol

NCT03327051

August 28, 2018

The Effect of Gastric Acid Suppression on Probiotic Colonization

BACKGROUND

A major role of gastric acidity is the digestion of food products and the elimination of potentially pathogenic bacteria that enter the gastrointestinal tract. The use of pharmacologic agents that reduce gastric acid secretion (i.e., H₂ receptor antagonists and proton pump inhibitors) has consequently been shown to influence the composition of the intestinal microflora.¹⁻³ Probiotics contain living microorganisms that are consumed for its putative benefits on the intestinal microbiota and intestinal health. However, despite widespread use of probiotics and acid suppressing effects, the effect of gastric acid suppression on the survival and colonization of probiotics organisms is currently unclear. We hypothesize that pharmacology-mediated gastric acid suppression will increase the colonization potential of probiotics. We propose to test this hypothesis in a randomized double-blinded placebo-controlled trial among healthy controls who initiate probiotics.

[figure not shown]
METHODS

- Study design: Randomized double-blind placebo-controlled trial
- Population: 15 + 15 healthy controls
- Exclusion criteria: any gastrointestinal condition, soy or gluten sensitivity, allergy to proton pump inhibitors, any chronic medical condition other than hypertension or hyperlipidemia, pregnancy, consuming herbs or probiotics
- Interventions
 - PPI (omeprazole 20 mg/day) + VSL #3 (900 billion bacteria)
 - VSL #3 (900 billion bacteria)
- Primary outcome
 - Quantitation of bacterial strains found in VSL #3 (*S. thermophilus*, *B. breve*, *B. longum*, *B. infantis*, *L. acidophilus*, *L. plantarum*, *L. paracasei*, *L. delbrueckii* subsp. *bulgaricus*)
- Secondary outcomes
 - Characterization of microbiota
 - Metabolome
 - Safety (reported symptoms)

Study Visits

- Timeline
 - Week -2: Run-in with either PPI or nothing x 2 weeks
 - Week 0: Initiation of VSL #3 x 4 weeks
 - Diet/symptom survey, blood, and stool collection at weeks -2, 0, and 4

Interested participants will be contacted on the phone and screened by the clinical research coordinator (CRC). If interested and eligible, the participant will be sent a stool collection kit by mail and scheduled for the initial study visit (Week -2).

Week -2

- Undergo formal informed consent process
- Complete baseline questionnaire
- Provide pre-collected stool
- Blood collection
- Receive and initiate blinded drug (PPI or placebo); no observation required
- Receive stool collection kit

Week 0

- Complete follow-up questionnaire
- Provide pre-collected stool
- Blood collection
- Receive and initiate VSL #3; no observation required
- Receive stool collection kit

Week 4

- Complete final questionnaire
- Provide pre-collected stool
- Blood collection

Drug Sourcing

- VSL #3, omeprazole, and placebo to be purchased from compounding pharmacy

Financial Considerations:

Payment

Research participants will be compensated [REDACTED] at completion of the study to cover travel expenses. A gift card may be used for human subject reimbursement.

Specimen Storage and Processing

Specimens will be collected, processed, and stored in the -80° freezer in the [name] Laboratory. Microbiome and metabolome analyses will be performed at a core facility.

Data Storage

Paper records will be stored in a secure, locked cabinet at the Stanford Center for Clinical Research. Electronic clinical data will be stored on a REDCap database hosted on Stanford IT-managed servers.

REFERENCES

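### The SAP's only named contrast is the week 0 to week 4 change within each arm; no between-arm test of the PPI effect is designated

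*Protocol*

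**What the plan says.** The Protocol's Background says that "the effect of gastric acid suppression on the survival and colonization of probiotics organisms is currently unclear" and hypothesizes that "pharmacology-mediated gastric acid suppression will increase the colonization potential of probiotics". It proposes to test this in a randomized, double-blind, placebo-controlled trial. Under Methods, the population is "15 + 15 healthy controls", both interventions include VSL #3, and people already taking probiotics are excluded. The primary outcome is "Quantitation of bacterial strains found in VSL #3", with no time point and no between-arm measure.

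Under Study Visits, the timeline has "Run-in with either PPI or nothing x 2 weeks", then "Week 0: Initiation of VSL #3 x 4 weeks", with "Diet/symptom survey, blood, and stool collection at weeks -2, 0, and 4". At each visit the participant's task is "Provide pre-collected stool", and VSL #3 is first handed out at the Week 0 visit. Week 4 is the last visit listed.

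The SAP, one paragraph dated December 2019 and largely in the past tense, sums the relative abundance of the VSL #3 strains. It applies a two-way ANOVA with a Bonferroni posttest and takes p below 0.05 as significant. The one comparison it describes, in parentheses, is the change from week 0 to week 4 within a group. It does not name the two factors, does not say whether participant is a repeated unit, and names no between-arm estimate or confidence interval.

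**The concern.** The hypothesis is about what acid suppression adds, so it is answered by comparing the arms. The named contrast asks something else: whether abundance rose within an arm once VSL #3 was started. A rise can be expected in both arms because both swallow the strains, whether or not the PPI does anything.

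Two misreadings follow. A significant rise in the PPI arm could be taken as support for the hypothesis when intake alone is enough to produce it. Or a significant rise in the PPI arm beside a non-significant one in the placebo arm could be taken as a PPI effect, although the difference between the arms was never tested. The randomized comparison that would answer the question is available in the data, but the SAP does not designate it.

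**Working it through.** **Inputs from the documents.** 15 per arm; VSL #3 in both arms; stools at weeks -2, 0 and 4; alpha 0.05; two-way ANOVA with Bonferroni posttest; named contrast within group, week 0 to week 4. The documents give no SD, effect size, power or dropout, so there is no planned figure to reproduce.

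**Assumptions.** Changes are normal with SD 1, so sizes are in SDs of the change. The true mean rise d is the same in both arms (no PPI effect). Tests are two-sided, and the Bonferroni family is the two within-arm comparisons. None of these is stated in the SAP.

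**Step 1: repeated-measures model.** With the residual pooled over arms (s², 28 df):

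- within-arm test: t = mean change / √(s²/15), critical value 2.368 (alpha 0.05/2);
- arm-by-time test: t = difference in mean change / √(2s²/15), critical value 2.048.

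Results from 200,000 simulated trials per row:

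| Equal rise d | PPI arm only significant | Both arms significant | Arm-by-time rejects |
|---|---|---|---|
| 0.5 SD | 21% | 13% | 5% |
| 1.0 SD | 7% | 86% | 5% |
| 1.5 SD | under 0.1% | 99.9% | 5% |

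A hand check treats the arms as independent. At d = 0.5 each arm is significant in 34.6% of trials, and 0.346 × 0.654 = 0.226. At d = 1.0 the figure is 92.8%, and 0.928 × 0.072 = 0.067. Both are close to the simulated values; the small gap arises because the two tests share s². The PPI-arm-only pattern peaks at about 24%, near d = 0.6. The both-arms column is simply power to detect a real rise from intake. It is not an error rate and says nothing about the PPI.

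**Step 2: if the ANOVA ignores pairing.** An ordinary two-way ANOVA (56 df) uses the between-person variance. With SD of change 1 and within-person correlation ρ, that variance is σ² = 1/[2(1 − ρ)]. The standard error used for arm-by-time is √(4σ²/15) and the true one is √(2/15), a ratio of true to used of √(1 − ρ): 0.89, 0.71 and 0.55 for ρ = 0.2, 0.5 and 0.7. Simulated at d = 1.0:

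| Assumed ρ | PPI arm only significant | Arm-by-time rejects |
|---|---|---|
| 0.2 | 9% | 3% |
| 0.5 | 18% | 0.7% |
| 0.7 | 21% | under 0.1% |

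Without pairing, the misleading pattern becomes more frequent than the 7% of Step 1, and the test that should be used becomes far too conservative.

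**Step 3: what the between-arm test can deliver at 15 + 15.** Arm-by-time over two time points is a two-sample t test on change, 28 df.

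- Detectable difference at 80% power: 1.06 SD by noncentral t. The normal approximation gives (1.960 + 0.842) × √(2/15) = 2.802 × 0.365 = 1.02 SD.
- Expected 95% CI half-width: 2.048 × √(2/15) = 2.048 × 0.365 = 0.75 SD.

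**Step 4: stool schedule against the VSL #3 course.** Weeks -2 and 0 precede VSL #3: 2 of 3 stools. Week 4, collected before the visit, falls at or just before the end of the course: 1 of 3. None follows it: 0 of 3. No collection window is given, so the time since the last dose is unknown.

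**The case against.** The strongest reply is that a two-way ANOVA with arm and time as factors already contains the arm-by-time term, and the SAP's wording suggests those factors. This is fair, and a reader who inferred that the SAP cannot test the PPI effect would go too far. What stands is narrower: the factors are not named, the term is not designated, and the comparison that is spelled out answers a different question.

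A second reply is that the misleading pattern fades as the rise grows. That is true under the repeated-measures model: with a large rise both arms are significant, and few readers would see a PPI effect in that. But the size of the rise is unknown, and neither outcome of the within-arm tests estimates the PPI effect.

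A reader might also infer that the design is faulty for want of a stool after the VSL #3 course. The documents do not support that. Colonization is not defined, the hypothesis speaks of its potential, the Background names survival as well, the primary outcome is worded neutrally as quantitation, and no passage claims persistence. A randomized week-4 comparison is valid for recovery during supplementation. The schedule therefore limits what may be said about the result; it does not make the plan wrong.

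**Conclusion.** The point holds as a gap in the stated analysis. The hypothesis is between arms, the only named contrast is within arms, and both arms take VSL #3. This follows from the texts and needs no assumption.

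The size does rest on assumptions. With an equal rise in both arms and no PPI effect, significance in the PPI arm only would appear in about 21%, 7% or under 0.1% of trials at rises of 0.5, 1.0 or 1.5 SD of the change, against 5% for arm-by-time under a repeated-measures model. If pairing is ignored, with ρ from 0.2 to 0.7 and a 1 SD rise, the pattern appears in about 9% to 21% and arm-by-time rejects in about 3% down to under 0.1%. The rise, the correlation, the Bonferroni family and normality are all assumed.

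One further inference should be avoided. The 1.06 SD detectable difference does not mean that smaller differences can never be excluded: with a half-width of about 0.75 SD, an estimate near zero would exclude differences beyond roughly 0.75 SD.

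**What to change.** 1. Name arm and time (week 0, week 4) as the ANOVA factors, with participant as the repeated unit. Make arm-by-time the test of the hypothesis and report the between-arm difference in change with its 95% CI. Week-4 abundance compared between arms, adjusted for week 0, is an acceptable alternative; choose one as primary.
2. Keep the within-arm changes as description. Do not read them, or significance in one arm only, as a PPI effect or as colonization.
3. Describe the week-4 result as recovery of VSL #3 strains during supplementation, and state that persistence was not tested.
4. Week 0 comes after two weeks of blinded drug, so it is not a pre-drug baseline. Repeat the comparison from week -2 as a sensitivity analysis, but only if those stools were assayed; the documents do not show that they were.
5. If data are already in hand, as the SAP's past tense suggests, date the change and label it post hoc.

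The cost is small: one model term and its interval from the week 0 and week 4 data the SAP already uses, plus wording. No participants, samples or assays are added. The downsides are a narrower claim than the title suggests, a post hoc label if it applies, and an interval that will be wide at 15 + 15.

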# The Effect of Gastric Acid Suppression on Probiotic Colonization

## Statistical Analysis Plan

NCT03327051

December 13, 2019

The relative percentage abundance was obtained by summing the levels of VSL#3 probiotic strains detected in the study samples. Statistical analysis was performed using GraphPad prizm. Two-way ANOVA with Bonferroni posttest was used for multi-variable analyses (within-group differences between week 0 and week 4). A p-value of <0.05 would be considered statistically significant.

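### The only contrast the SAP names is within arm, on a summed relative abundance with no stated denominator; the hypothesis needs a between-arm test of that sum, strain results beside it, and a conclusion worded as share

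*SAP*

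**What the plan says.** In the protocol (METHODS, Primary outcome) the outcome is "Quantitation of bacterial strains found in VSL #3", followed by eight organisms. No unit, assay, scale (absolute or relative) or summary measure is given. The hypothesis (BACKGROUND) is that acid suppression "will increase the colonization potential of probiotics". Both arms receive VSL #3 and one also receives omeprazole; the population is "15 + 15 healthy controls". Blinded drug starts at week -2 and VSL #3 at week 0. Exclusions include people "consuming herbs or probiotics".

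The SAP is one paragraph. Its outcome variable is given in this sentence: "The relative percentage abundance was obtained by summing the levels of VSL#3 probiotic strains detected in the study samples". Its method is this: "Two-way ANOVA with Bonferroni posttest was used for multi-variable analyses", with the parenthesis "within-group differences between week 0 and week 4". The significance level is 0.05. The SAP does not say what the percentage is a percentage of, how an undetected strain is counted, or what the two ANOVA factors are.

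**The concern.** The trial asks whether VSL #3 organisms colonise better with acid suppression than without it. That is a difference between arms. A change from week 0 to week 4 inside an arm shows what VSL #3 did in that arm. Both arms take VSL #3, so both may rise, and a significant rise in one arm but not in the other is not a test of the difference between them.

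The variable adds two limits on interpretation once the arms are compared. A pooled sum does not show which strains differ, and opposing differences can cancel. A relative abundance also depends on the other organisms in its denominator, so a higher share may mean more VSL #3 organisms or fewer of everything else. From the summed share alone a reader could not separate these, yet the hypothesis is about colonization.

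**Working it through.** The plan gives no effect size, SD, power or abundance figure, so there is none of its own to reproduce. Every abundance and effect size below is assumed; only the eight strains, 15 per arm and the 0.05 level come from the documents. The tests are taken as two-sided because the SAP does not say.

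1. **Contrast named against contrast needed.** The protocol's hypothesis is PPI plus VSL #3 against VSL #3. The SAP's named contrast is week 0 against week 4 within group. If the ANOVA factors are group and time, which is the likelier reading after the summing sentence, the model contains a group-by-time term, but the SAP does not name it as a test. If the factors are strain and time within each group, strains are analysed but the arms are not compared.

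2. **Masking in a between-arm comparison.** Let one strain make up a fraction p of the control-arm sum, and let the other seven be twice as high in the PPI arm. The sums are equal if the main strain is lower by (1 - p)/p:
   - p = 0.6: 0.4/0.6 = 67%
   - p = 0.8: 0.2/0.8 = 25%
   - p = 0.9: 0.1/0.9 = 11%

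   With equal strains, eight at 0.25% sum to 2.0%; four at 0.50% and four at 0 also sum to 2.0%.

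3. **Share against amount.** Assume the denominator is all bacteria and VSL #3 counts are equal in the two arms. Let r be the control-arm share and f the load of other bacteria in the PPI arm relative to control. The PPI-arm share is r/(r + (1 - r)f). For r = 5%:
   - f = 1: 5.0%
   - f = 0.8: 0.05/0.81 = 6.2%
   - f = 0.5: 0.05/0.525 = 9.5%
   - f = 1.2: 0.05/1.19 = 4.2%
   - f = 1.5: 0.05/1.475 = 3.4%

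   Over f = 0.5 to 1.5, r = 1% gives 1.98% to 0.67%, and r = 10% gives 18.2% to 6.9%.

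4. **Where these effects apply.** VSL #3 starts at week 0 and probiotic users are excluded, so low week 0 levels are foreseeable. A strain near zero has no room to fall, and zero over any denominator is zero. Within an arm, then, opposing changes could not hide a rise, and a changed denominator could alter its size but not create it. Between arms, a zero week 0 level protects nothing. With r = 1% and f = 0.5, the change from zero is 1.0 point in control and 0.01/0.505 = 1.98 points under PPI.

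5. **Precision of strain results at 15 per arm.** The 95% CI half-width for a difference is 2.048 × √(2/15) = 0.748 SD. For an assumed 1 SD difference, t-test power is 75% at 0.05 and 43% at 0.05/8 = 0.00625. For detection rates of 80% against 40%, Fisher exact power is 45% and 19% at those two levels. Eight unadjusted tests would carry a family-wise error of 1 - 0.95^8 = 0.337 if independent.

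**The case against.** The best case for the plan has four parts.

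- **Summing is a sound choice.** The hypothesis speaks of probiotics collectively, and one endpoint avoids the 0.337 family-wise error of eight unadjusted tests. This stands, and the sum should stay.
- **Masking and the denominator have little force for the contrast the SAP names.** If week 0 levels are near zero, this stands too. The two limits matter for the between-arm comparison that the hypothesis requires, or if week 0 levels turn out to be substantial.
- **The two-week run-in puts any stable effect of acid suppression on the background flora at both ends of the within-arm contrast.** That helps only where week 0 levels are measurable. Step 4 shows that nothing cancels between arms when week 0 is zero.
- **All magnitudes are assumed.** This stands, and the figures are illustrations only.

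A reader might infer that the SAP rules out strain-level analysis. It does not: the factors are unnamed, so such an analysis is neither stated nor excluded. A reader might also infer a distorted share from the protocol's remark that acid suppression "has consequently been shown to influence the composition of the intestinal microflora". Composition is not load, and a reshuffle of other bacteria at constant load leaves the VSL #3 share unchanged. The documents support no particular size or direction.

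**Conclusion.** The concern holds in a limited form. The SAP names no test of the between-arm hypothesis, and its single defined variable has no stated denominator. When that variable is compared between arms, a null result could conceal opposing strain differences, and a positive one could not by itself be read as more VSL #3 organisms. How large either effect would be cannot be computed from the documents. The illustrations rest on an assumed dominant strain, an assumed share and an assumed difference in load, with all bacteria as the denominator.

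It would go too far to call the trial biased. A randomised comparison of shares remains a valid comparison of shares; what is limited is what it says about amount, and about which strains. The change is worth making because it aligns the main test with the hypothesis at almost no cost. Confidence is medium, since the unnamed ANOVA factors might already cover part of it.

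**What to change.** 1. Keep the sum as the single main summary. State its denominator, how undetected strains are counted, and the two ANOVA factors.
2. Make the between-arm comparison of the sum the main test, either as the group-by-time term or as week 4 by arm, and say which. The within-arm changes can be shown beside it.
3. Report each of the eight strains by arm, as level and detection rate with 95% CI, as supporting estimates. If they are tested, use Holm adjustment; if they were added after the data were seen, label them post hoc. This addresses masking only.
4. Unless an absolute count or total bacterial load is available, word the conclusion as relative share of the stated denominator, not as amount.

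**Cost.** No new samples are needed: the sum is built from strain levels already measured, and microbiome analysis at a core facility is already in the protocol (Specimen Storage and Processing). The SAP is written in the past tense, so added strain tests may have to be labelled post hoc. Strain-level precision is low at 15 per arm, so those results are best read as estimates. The conclusion also becomes narrower, a statement about share.

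### Pre-specification of the SAP's endpoint and test is not documented: both first appear in a December 2019 text that reports them as already done

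*SAP*

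**What the plan says.** The protocol is dated "August 28, 2018" and has no statistical section. Under Methods, the primary outcome reads "Quantitation of bacterial strains found in VSL #3", followed by a list of eight organisms. Stool is collected at weeks -2, 0 and 4, and no week is designated for the primary outcome. The Background section states the hypothesis, that acid suppression increases colonization, and proposes to test it in a randomized, double-blind, placebo-controlled trial with 15 participants per arm.

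The SAP is one paragraph dated "December 13, 2019". It has four sentences:

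- Endpoint: "The relative percentage abundance was obtained by summing the levels of VSL#3 probiotic strains detected in the study samples".
- Software: "Statistical analysis was performed using GraphPad prizm".
- Test and contrast: "Two-way ANOVA with Bonferroni posttest was used for multi-variable analyses (within-group differences between week 0 and week 4".
- Threshold: "A p-value of <0.05 would be considered statistically significant".

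The first three are in the past tense. Only the threshold is conditional. Neither document gives a date for the last sample, the assay, database lock, unblinding or the first analysis, and neither cites an earlier analysis plan.

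**The concern.** Past tense in a SAP is often only a matter of style, because the protocol has already fixed the analysis. Here it has not. The only written record of how strain counts become one number, and of how that number is tested, is a text that describes the work as finished and speaks of strains already detected in the samples.

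What is at stake is the meaning of the 5% threshold. It holds for an endpoint and test fixed before the results are seen. If the summary, scale, time point, contrast or test was settled with results in view, the true false-positive rate is higher by an unknown amount, and a significant finding generates a hypothesis rather than testing one. The named contrast adds to the doubt. The hypothesis concerns a difference between randomized arms, while the SAP names only a change within each arm. The SAP's test therefore does not follow so directly from the protocol that a reader can assume it was always intended.

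**Working it through.** **Step 1: what each document fixes.**

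| Element | Protocol | SAP |
|---|---|---|
| Organisms | Eight, by name | VSL #3 strains detected |
| Summary | Not stated | Sum |
| Scale | Not stated | Relative percentage abundance |
| Time point | Three sampling weeks, none designated | Weeks 0 and 4 |
| Contrast | Not stated; between arms is implied by hypothesis and design | Within group |
| Test | Not stated | Two-way ANOVA, Bonferroni posttest |
| Significance level | Not stated | 0.05, sidedness not stated |

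Of the seven elements, the protocol fixes the first. The other six are first written down in the SAP.

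**Step 2: the gap.** August 28, 2018 to August 28, 2019 is 365 days. From there to December 13, 2019 is 31 + 30 + 31 + 15 = 107 days. The total is 472 days, and 472 / 30.4375 = 15.5 months.

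**Step 3: what an open choice could do to a nominal 5%.** The documents give no false-positive calculation to reproduce, and no variances or correlations, so this step is an illustration on assumptions. Null trials were simulated with 15 per arm (from the protocol) and eight lognormal strains (assumed log-SD 1.5, assumed common correlation 0.3, 0.5 or 0.7), using two-sample tests between arms. The sum was tested in three ways: t-test on the raw scale, t-test on the log scale, and rank test. The rate is the share of null trials in which the smallest available p-value is below 0.05.

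| Open to choice after the data | Corr. 0.3 | 0.5 | 0.7 | Range over repeated runs |
|---|---|---|---|---|
| Nothing | 0.05 | 0.05 | 0.05 | by definition |
| Which of three tests of the sum | 0.065-0.077 across the three | | | 0.060-0.077 |
| The above, or any strain on the raw scale | 0.21 | 0.19 | 0.15 | 0.15-0.21 |
| The above, or any strain on the log scale | 0.31 | 0.26 | 0.21 | 0.19-0.32 |

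**Step 4: cross-check.** With the eight strains and their sum treated as nine independent tests, the rate is 1 - 0.95^9 = 1 - 0.630 = 0.370. A separate simulation with one t-test per endpoint on normal data (10,000 runs) gave 0.36, 0.30, 0.22 and 0.12 at correlations 0, 0.3, 0.6 and 0.9. In the same runs the sum alone, tested once, gave 0.048-0.052. The inflation therefore comes from choosing among endpoints, not from the test itself.

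**The case against.** The strongest reply is that tense shows when a text was worded, not when a decision was made. The SAP does not say whether December 13, 2019 is the day the plan was first written or the date of this version, and no assay, lock or unblinding date is given. A reader might infer that the endpoint was picked after the results were seen. The documents do not show that, and an earlier dated plan, if one exists, would answer the point. This part of the reply stands. It limits the conclusion to missing documentation.

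Three further limits also stand.

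- The SAP never calls its analysis confirmatory or pre-specified. It states a threshold, in conditional wording. The point concerns how a result may be presented, not a claim the SAP makes.
- It would be wrong to say that the protocol left the choice of strains open, since it names eight. What it left open is the summary, scale, time point, contrast, test and significance level.
- The simulated rates are not the error rate of this plan. They come from between-arm tests, while the SAP names within-group contrasts from a two-way ANOVA with a Bonferroni step, which was not simulated. The upper figures also require that a single strain could have become the reported result, whereas the SAP reports the sum.

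None of this supplies evidence that the endpoint and test were set in advance.

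**Conclusion.** The point holds as a gap in documentation. The outcome domain was set in August 2018. The summed relative abundance, the week 0 to week 4 within-group contrast and the two-way ANOVA are first recorded in a December 2019 text that reports them as done. A p-value below 0.05 from that analysis cannot be presented as a pre-specified result on these documents.

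The size cannot be known from the documents. Under the stated assumptions (between-arm tests, 15 per arm, log-SD 1.5, correlations 0.3 to 0.7), the false-positive rate is 5% if nothing was selected, about 6-8% if only the test of the sum was chosen after the data, and about 15-32% if any single strain could also have been reported. A reader might take the top of that range as the plan's actual error rate, or as a sign of selective reporting. It is neither, because the documents are equally compatible with 5%.

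**What to change.** If a dated analysis plan earlier than December 13, 2019 exists, cite it, and state when the stool results were first seen and when the blind was broken, because an earlier plan settles the matter only if it precedes both. If no such plan exists, label the summed-abundance ANOVA post hoc and word its conclusion as exploratory.

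In either case, report beside it the between-arm comparison that the protocol's hypothesis implies, for the sum and for each of the eight named organisms, whatever the results. Give estimates with confidence intervals and adjust for multiplicity across the eight, for example by Holm. The first Holm step is 0.05 / 8 = 0.00625, which is demanding with 15 per arm, so the intervals will carry most of the information. Do not describe this comparison or its adjustment as fixed in 2018, because the protocol names the organisms but specifies neither.

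The cost is some wording in the SAP and the results report, and one extra table from data the trial already collects. The downside is a weaker headline claim.

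### The SAP names only a within-group week 0 to week 4 contrast and designates no between-arm test, although the hypothesis compares PPI with control

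*SAP*

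**What the plan says.** The Protocol's Background states the question: "We hypothesize that pharmacology-mediated gastric acid suppression will increase the colonization potential of probiotics". It continues: "We propose to test this hypothesis in a randomized double-blinded placebo-controlled trial among healthy controls who initiate probiotics". Under Methods, the size is given as "Population: 15 + 15 healthy controls". One arm receives "PPI (omeprazole 20 mg/day) + VSL #3 (900 billion bacteria"); the other receives VSL #3 at the same dose without the PPI.

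The Study Visits timeline starts the probiotic for everyone at the same point: "Week 0: Initiation of VSL #3 x 4 weeks". The Week 0 visit list agrees: "Receive and initiate VSL #3; no observation required". Samples are scheduled as "Diet/symptom survey, blood, and stool collection at weeks -2, 0, and 4".

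The Protocol has no statistical section, and its primary outcome carries neither a time point nor a comparison. The SAP is a single paragraph. It sums the VSL #3 strains into one relative abundance, sets significance at p < 0.05, and describes the test as "Two-way ANOVA with Bonferroni posttest was used for multi-variable analyses (within-group differences between week 0 and week 4". It does not name the two ANOVA factors, an arm effect, an arm-by-time interaction, or an arm comparison at week 4.

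**The concern.** The contrast that the SAP names does not answer the question the trial was randomized to answer. Both arms begin VSL #3 at week 0, so summed VSL #3 abundance can rise by week 4 in each arm whether or not the PPI does anything. Only a comparison between the arms uses the randomization to separate the PPI from the probiotic.

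Two errors are then possible.

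- **False claim.** One arm is significant, the other is not, and a reader takes this as a PPI effect. The SAP does not say it will be read this way, but it offers no other rule, so the reading stays open.
- **Missed effect.** Both arms rise clearly, both within-arm tests are significant, and a real difference between them goes unreported.

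**Working it through.** The plan states no power, SD, effect size or dropout, so there is no figure of its own to reproduce. The omission is established from the text. The arithmetic below only illustrates what it can lead to.

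**Inputs from the documents:** 15 per arm (Protocol, Methods); alpha 0.05 (SAP); contrast week 0 to week 4 within group (SAP).

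**Assumptions:** two-sided tests; normal changes; equal SDs, with the SD of the week 0 to week 4 change set to 1; pooled error with df = 2 × 15 − 2 = 28; Bonferroni over two contrasts, one per arm.

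**Critical values.** Within arm: t(1 − 0.05/4, 28) = t(0.9875, 28) = 2.368. Between arms: t(0.975, 28) = 2.048.

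**1. Equal rises, no PPI effect.** Let the true rise be δ in both arms and s the pooled SD, with s² distributed as χ²(28)/28. Given s, the chance of a significant rise in one arm is p(s) = P(Z > 2.368·s − δ√15). The arm means are independent, so the chance that only the PPI arm is significant is the average of p(s)·[1 − p(s)] over s.

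| True rise δ in both arms (SD) | Only the PPI arm significant |
|---|---|
| 0.2 | 6.1% |
| 0.4 | 16.5% |
| 0.6 | 23.6% (about the maximum) |
| 0.8 | 17.2% |
| 1.0 | 6.6% |
| 1.2 | 1.4% |
| 1.5 | 0.05% |

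A direct between-arm test rejects in 5% of such trials whatever δ is, with 2.5% favouring PPI. With right-skewed changes (shifted lognormal, SD 1, 100,000 simulated trials), the PPI-only range is 0.05% to 29.2% at log-SD 0.5 and 0.7% to 24.8% at log-SD 1.0. The between-arm test then rejects in 4.6% and 3.6%.

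**2. An apparent PPI effect without support.** Observed rises are 0.7 SD on PPI and 0.5 SD on control.

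- PPI: t = 0.7 × √15 = 2.711, adjusted p = 0.023.
- Control: t = 0.5 × √15 = 1.936, adjusted p = 0.126.
- Difference: t = 0.20/√(2/15) = 0.548, p = 0.588.
- 95% CI: 0.20 ± 2.048 × √(2/15) = 0.20 ± 0.748, or −0.55 to 0.95 SD.

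**3. A difference the named contrast does not show.** Observed rises are 2.06 SD on PPI and 1.0 SD on control.

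- PPI: t = 2.06 × √15 = 7.978, adjusted p < 0.001.
- Control: t = 1.0 × √15 = 3.873, adjusted p = 0.0012.
- Difference: t = 1.06/√(2/15) = 2.903, p = 0.0071.
- 95% CI: 1.06 ± 0.748, or 0.31 to 1.81 SD.

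**4. What a between-arm test can detect.** Power comes from the noncentral t with df 28 and noncentrality d·√(15/2).

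| True difference d (SD of change) | Power |
|---|---|
| 0.5 | 26.2% |
| 0.8 | 56.2% |
| 1.06 | 80.0% |

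**The case against.** The strongest reply is that a two-way ANOVA already contains the right test. The strains are summed into one outcome and there is one randomized grouping, so the natural factors are arm and time. That model yields an arm-by-time interaction, and the parenthesis may describe only the posttest. This stands in part: a between-arm test is available under the named model, and it would be wrong to call it impossible. But the SAP does not name the factors, and the only comparison it spells out is within group. It gives a 0.05 threshold without tying it to a term that addresses the PPI. A term the software may print is not a designated test.

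A second reply is that the false-claim percentages apply only if someone infers a PPI effect from significance in one arm, which the SAP never proposes. They also depend on an assumed common rise, an assumed error structure and an assumed number of contrasts. This stands: the percentages illustrate a general point and do not estimate this trial's error rate. For common rises above about 1.2 SD the false-claim risk nearly vanishes, and only the missed-effect problem remains.

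A third reply is that the SAP, dated December 13, 2019, is written in the past tense, so a change may come too late to count as prespecification. That limits what an edit can achieve but does not remove the defect.

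**Conclusion.** The concern holds. The SAP's only named contrast is within group, and neither document designates a between-arm test of a hypothesis that is wholly about a between-arm difference. Carrying out that contrast alone would leave the trial's question unanswered. This must be fixed, and confidence is high because the conclusion rests on the text and not on any assumed number.

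The size is illustrative. Reading PPI-only significance as a PPI effect would be wrong in up to about 24% of null trials under normal changes, or up to about 29% under the skewed distributions tried, against 2.5% for a direct test. At larger common rises the risk shifts to missing a real difference.

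**What to change.** Revise the SAP in one or two sentences.

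- Name the factors: arm, and time as a repeated measure.
- Designate one between-arm primary test at two-sided alpha 0.05, reporting the PPI-minus-control estimate and 95% CI for summed VSL #3 abundance. Either the arm-by-time interaction or an ANCOVA of week-4 abundance adjusted for an earlier value is acceptable; choose one.
- If the interaction is chosen, state that it uses weeks 0 and 4 only. Adding week −2 makes it a 2-degree-of-freedom test without a single estimate.
- State the baseline and why. Week 0 precedes the probiotic but follows two weeks of PPI or control, so it targets change after any run-in shift. Week −2 precedes all assigned treatment, so it targets the total PPI effect.
- Label within-arm changes descriptive and draw no PPI conclusion from them.
- If the analysis has already been done, state that the between-arm test was specified afterwards.

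The cost is the edit and one re-run on stool data that the Protocol already schedules. There are three downsides. A within-arm p-value can no longer support a PPI claim. With 15 per arm the test of change reaches 80% power only at about 1.06 SD, with a 95% CI of about ±0.75 SD. ANCOVA may help somewhat: in 40,000 simulated trials it reached about 80% power at 1.08 SD of week-4 abundance with baseline correlation 0, and at 0.94 SD with an assumed correlation of 0.5. Finally, if results are already known, no edit restores prespecification.
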